#### Section IV. Patient Protections and Methods to Minimize Risk

- A. Risks to Human Subjects
- a. Human Subjects Involvement, Characteristics, and Design

The focus of this research is to implement and determine the feasibility and efficacy of an intervention that is based on the Diabetes Prevention Program (DPP) and includes intensive breastfeeding support and counseling in a cohort of overweight or obese pregnant women to be followed during pregnancy through 6 months postpartum. Study participants will be pregnant women who reside in or near Wichita and in or near Lakin, Kansas. Participants are eligible if they meet study inclusion criteria. This is a randomized controlled pilot study with three study arms. Participants will be randomized to each arm of the study by computer. Participants in Tx1 will receive the DPP plus breastfeeding, participants in Tx2 will receive the DPP only, and participants in Tx3 will receive usual care. Usual care consists of (1) the same obstetrical care that pregnant women with normal body mass index (BMI) receive, and (2) obstetrical care that is provided to pregnant women by the same provider ([name]). Total enrollment for the proposed study will be 60 pregnant female participants.

Participants are recruited from an obstetrical clinic at Via Christi Hospitals Wichita, Inc., a regional medical center located in Wichita, Kansas, and Kearny County Hospital, a critical access full-spectrum rural hospital, in Lakin, Kansas. Participants must be women 18 years old or older, pregnant, with a BMI ≥ 25 and <35, and able to read and understand English. Eligible participants will be recruited during the 1st trimester or early during the 2nd trimester. General study exclusions include women who have pregnancy complications that require emergency care, have thyroid disease, have multiple gestation, had substance abuse within last 3 years, have an ART (Assisted Reproductive Technology) pregnancy, are a current smoker, had prior bariatric surgery, have been in a weight-loss program within 3 months of conception, have a BMI ≥ 35, are unable to attend intervention/follow-up visits, are unwilling to self-monitor data collection, are unable to complete the intervention, have a presence of any condition that limits walking, have a presence of any condition that limits following diet recommendations, or have a pregnancy complicated with a fetus diagnosed with lethal malformations/conditions.

Vulnerable populations in this study might include economically/educationally disadvantaged persons. Some pregnant women may be economically and/or educationally disadvantaged based on their demographic profile. We especially want to accommodate these individuals as our study's focus is on measuring postpartum weight, breastfeeding behaviors, HbA1c and blood pressure among an at-risk ethnically and racially diverse, overweight and obese pregnant population.

We will obtain approval from the Institutional Review Board (IRB) at the University of Kansas School of Medicine-Wichita (KUSM-W), Via Christi Hospitals Wichita, Inc. (VCH), and Kearny County Hospital (KCH). Via Christi Hospitals Wichita, Inc. and Kearny County Hospital are agreeable to allow [name] and her research team access to use their patient population to recruit study participants. With the active assistance of [name], maternal fetal medicine specialist at both hospitals, [name] and her research team will recruit each participant for the study. All members of the research team involved in consenting and enrolling participants have successfully completed institutional Human Subjects training.

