### C. Number of Participants

This IRB protocol pertains to the recruitment of eligible participants from two obstetrical clinics: one clinic at Via Christi Health (VCH), a regional hospital in Wichita, and another clinic at Kearny County Hospital, a full-service hospital in rural southwest Kansas. About 45% (16,797) of Wichita's Hispanic population is female and of reproductive age, 102 and the VCH clinic sees a high volume of this at-risk population at an average of 123 pregnant patients per month, with an average pre-pregnancy BMI of 30.5 (personal communication by senior management staff at VCH on January 18, 2017). These socio-demographic and health data are similar to those of atrisk rural pregnant women in southwest Kansas who visit Kearny County Hospital (KCH) for prenatal and postnatal care. [name], maternal fetal medicine specialist, sees pregnant women at both of these locations (VCH and KCH), and he and his staff will actively assist with patient recruitment. Our goal is to randomize a total of 72 eligible participants (24 women in each study arm, which translates to 12 women from each recruitment site). Our recruitment target of overweight or obese pregnant women will involve 50% Hispanic women (who are English-speaking) and 50% other race including non-Hispanic whites. The population of pregnant women in southwest Kansas who deliver at Kearny County Hospital, Lakin, Kansas, is estimated to be 300 individuals, of which 75% (or 225 individuals) have a BMI  $\geq$  25 and  $\leq$  35.

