### D. Subject Selection Criteria and Recruitment

We will recruit pregnant patients from two obstetrical clinics: one clinic at Via Christi Hospitals Wichita, Inc. (VCH), a regional hospital in Wichita, and another clinic at Kearny County Hospital, a full-service rural hospital located in Lakin, southwest Kansas. [name], maternal fetal medicine specialist, sees pregnant women at this location, and he and his staff will actively assist with patient recruitment. During the first prenatal appointment, [name] will screen potential participants for inclusion criteria, and if he believes a participant meets inclusion criteria (see Table 1), then he will familiarize a potential participant with the study's purpose. If the potential participant is interested in the study, then he will give her a study brochure and a hard copy of the consent form. Prior to using this study brochure, the brochure will be reviewed and approved by the IRB at Via Christi Hospitals Wichita, Inc. By providing the potential

participant with a copy of the consent form, this will serve as the verbal consent script. [name] will also provide the potential participant's name and phone number to [name] and her research coordinator. After receiving a potential participant's name and phone number from [name], the research coordinator will follow up with a phone call to determine if the potential participant again meets study inclusion criteria, and if she does, the coordinator will screen if the potential participant meets study exclusion criteria during the same phone call (see Table 1). Before the research coordinator screens for inclusion and exclusion criteria, during this same phone call, verbal consent will be obtained between the participant and the research coordinator, using the consent form as the verbal consent script, and then written e-consent will be obtained via REDCap at the orientation session. Once the participant is enrolled in the study and over the course of her pregnancy develops one of the conditions mentioned under Exclusion (Table 1), then this will be reported to the Data and Safety Officer. It will then be decided in consultation with [name] if the participant will be able to continue participating in the study or if she will need to be dismissed.

Table 1. Enrollment Criteria

Inclusion
1. Pregnant
2. In 1st trimester or early in 2nd trimester
2. BMI ≥ 25 and < 35
3. At least 18 years old or older
Be able to understand English
5. Must have a cell phone

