6. Able to use Facebook
7. Able to use Skype, FaceTime or Zoom
Exclusion
Pregnancy complications that require emergency care
2. Thyroid disease
3. Multiple gestation
4. Substance abuse within last 3 years
5. ART (Assisted Reproductive Technology) pregnancy
6. Current smoker
7. Prior bariatric surgery
8. In weight-loss program within 3 months of conception
9. BMI ≥ 35
10. Unable to attend intervention/follow-up visits
11. Unwilling to self-monitor data collection
12. Unable to complete intervention
13. Presence of any condition that limits walking
14. Presence of any condition that limits following diet
recommendations
15. Pregnancies complicated with fetuses diagnosed with
lethal malformations/conditions

If the participant meets enrollment criteria, then the research coordinator will call her again to assign her a time and place for the orientation session, to complete study-related survey instruments, and to obtain her email address to provide her with informed consent materials for review. Participants are informed that they will earn incentives to continue and complete the study: (1) a \$50 gift card at study entry, (2) a digital scale and pedometer at delivery, and (3) a gift up to \$75 for baby at Walmart's baby registry at study closure. Investigators will issue incentives in accordance with policies set forth by

IRB (please refer to the heading titled "Self-Administered Surveys and Incentive to Participate" below for additional detail regarding participant incentives).

Our recruitment target of overweight or obese pregnant women will involve 50% Hispanic women (who are English-speaking) and 50% other race including non-Hispanic whites. We anticipate meeting our recruitment goals through multiple approaches. We will promote the study via targeted mailings and clinic posters. We will advertise and develop study materials in English only. We will recruit over a period of 9 months, planning to randomize 2-3 participants

each week, or 1-2 participants per site. Our goal is to randomize a total of 72 pregnant women (24 women in each study arm, 12 women per site). Given an attrition rate of 20%, this will leave us with 60 women total (20 women in each study arm, or 10 women per site in each study arm).

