Sample Size and Randomization. The primary outcomes of interest are: (1) postpartum weight loss; (2) HbA1c and mean arterial blood pressure; and (3) breastfeeding duration. A total of 60 participants (20 per study arm) will be recruited. The results from this pilot study will be used in sample size estimation for a future study that is sufficiently powered to detect a clinically meaningful effect size. Due to the nature of this project being a feasibility study, the sample size in the proposed study is not based on providing adequate power to detect a clinically meaningful effect size across the three study arms. Block randomization with block size of 5 participants will be employed. A sequence of 12 random integers will be generated using a computer algorithm. The first 4 integers of the sequence will be assigned to the DPP plus breastfeeding arm; the next 4 integers will be assigned to the DPP only arm; and the last 4 will be assigned to the usual care arm. Blocks will be assigned to arms in the increasing order of sequence of integers generated.

**Statistical Analysis.** For baseline data characteristics, descriptive statistics will be reported as mean and standard deviation for continuous variables and as count and percentage for categorical variables. Depending on the distribution of the continuous variables, the Kruskal-Wallis test or ANOVA will be used to test for differences in continuous variables across the three arms. Chi-

Square test of independence (or Fishers exact test if 25% of cells have counts less than 5) will be used to assess the association between categorical variables and the three arms. The analysis will be based on "intention-to-treat" principle. A two-sided alpha level of 0.05 will be used to determine statistical significance. A 95% confidence interval will also be reported.

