Aim 1: Test the efficacy of Tx1 to improve 6-month postpartum weight loss among women with a BMI  $\geq$  25. The outcome of interest is 6 month postpartum weight loss measured across the three arms. Weight will be measured at delivery, and at weeks 1, 3, and 6 postpartum and at 3 months (13 weeks) and 6 months (26 weeks) postpartum. The difference in postpartum weight (weight loss) between two consecutive time points will be computed. Thus, each participant has 5 postpartum weight loss values based on weight measurements at 6 different time points. We will use the generalized estimating equation approach to compare weight loss in the DPP plus breastfeeding arm (Tx1) with weight loss in the DPP only (Tx2) and usual care (Tx3) arms, as well as weight loss between Tx2 and Tx3. The working correlation matrix will be specified after assessing the data. The model will be adjusted for the effect of age, race/ethnicity, level of education, annual household income, family history of diabetes, baseline weight, pre-diabetes status, and parity.

Aim 2: Test the efficacy of Tx1 to improve 6-month postpartum mean blood glucose (HbA1c) and mean arterial blood pressure among women with a BMI  $\geq$  25. The outcome of interest is mean blood glucose (HbA1c) and mean arterial blood pressure ((systolic blood pressure +2 (diastolic blood pressure)/3)) measured at baseline, delivery, and at 6 months postpartum across the three arms. We will use a multiple linear regression approach to compare HbA1c in Tx1 with HbA1c in Tx2 and Tx3, as well as HbA1c between Tx2 and Tx3. The model will be adjusted for the effect of age, race/ethnicity, level of education, annual household income, family history of diabetes, pre-diabetes status, parity, and baseline weight. The difference in mean blood arterial pressure at 6 months postpartum will also be assessed using a separate multiple linear regression approach after adjusting for the same covariates listed previously.

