### C. Potential Benefits of the Proposed Research to the Subjects and Others

The potential benefit of this study is to determine if a combined breastfeeding, DPP-based intervention reduces postpartum weight, increases breastfeeding, and improves mean blood glucose (HbA1c) and mean arterial blood pressure, among an at-risk population with a BMI ≥ 25. This is an innovative way to address physical activity, weight, and breastfeeding in one intervention that is modeled after the evidence-based Diabetes Prevention Program and could be integrated into the continuum of healthcare services provided to culturally, diverse at-risk pregnant women. Results of the proposed intervention will inform the development of interventions aimed at reducing diabetes risk factors and potential progression to type 2 diabetes after pregnancy among at-risk women. The overall impact of this project will be to reduce diabetes risk factors among a high-risk population and inform interventions aimed at reducing these risk factors thereby decreasing disproportionate morbidity. Moreover, study results will add significant knowledge to the field of diabetes prevention and related behavioral health interventions and strategies to improve maternal and child health outcomes. Although the randomization process will not be performed by a clinician, instead it will be generated by a computer system, participants may still have concerns about bias (who receives the treatment versus who receives the control). We will inform them that, regardless of group assignment, they will continue to receive routine care from their maternal fetal medicine specialist.

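### Diabetes diagnosed before pregnancy is missing from both exclusion lists, and the Aim 2 model adjusts for neither existing diabetes nor baseline HbA1c, although HbA1c is a primary outcome

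*Combined protocol and SAP*

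**What the plan says.** **Outcome.** Section III, Sample Size and Randomization: "The primary outcomes of interest are: (1) postpartum weight loss; (2) HbA1c and mean arterial blood pressure; and (3) breastfeeding duration". Section IV.C says the results should inform work on "potential progression to type 2 diabetes after pregnancy among at-risk women".

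**Eligibility.** Table 1 (Section II.D) and the prose list in Section IV.A.a give the same 15 exclusions. The prose version covers women who "have thyroid disease, have multiple gestation, had substance abuse within last 3 years, have an ART (Assisted Reproductive Technology) pregnancy" and goes on to smoking, bariatric surgery, BMI and others. Neither list mentions type 1 or type 2 diabetes or sets an HbA1c or glucose limit. Because the two lists agree item by item, the omission is not a lost line in one table. The nearest items are general: complications needing emergency care, inability to complete the intervention, and a condition that limits following dietary advice.

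**Analysis.** The Aim 2 regression compares HbA1c between arms. Its covariates are age, race/ethnicity, education, income and "family history of diabetes, pre-diabetes status, parity, and baseline weight". Pre-diabetes status is not defined. Table 5 schedules HbA1c and glucose tolerance at baseline, but neither serves as an eligibility test and baseline HbA1c is not a covariate.

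**Numbers.** Section III: "A total of 60 participants (20 per study arm) will be recruited". Section II.C: "Our goal is to randomize a total of 72 eligible participants", which is 24 per arm. Section II.D links the two: "Given an attrition rate of 20%, this will leave us with 60 women total".

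**The concern.** Women with established diabetes lie outside the group whose progression to diabetes the programme hopes to prevent, and their HbA1c can sit well above that of the other participants. With about 20 women per arm, one or two such values can move an arm mean and widen the residual variance. Two things are at stake. The Aim 2 comparison could partly reflect which arm happened to receive such a woman. And Section III says the pilot will feed the sample-size calculation of a later trial. If that trial excludes women with diabetes, an HbA1c variance that includes them would be too large for it.

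**Working it through.** The plan states no HbA1c SD, standard error, effect size or power, so there is no figure of its own to reproduce.

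**Inputs from the documents.** Three arms, n = 20 per arm (24 per arm as the randomisation target), linear regression, covariates as listed above.

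**Assumed inputs.** SD of HbA1c without diabetes s = 0.3 to 0.5 points. Gap between a woman with diabetes and the others at 6 months d = 1.0 to 3.0 points. Prevalence among enrolled women 1%, 2% or 5%.

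**1. Clean standard error of a between-arm difference:** s × √(2/20).
- s = 0.3: 0.095
- s = 0.4: 0.126
- s = 0.5: 0.158

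**2. One such woman in one arm only.** Her arm's mean moves by d/20: 1.0/20 = 0.05 to 3.0/20 = 0.15. Relative to the clean standard error this runs from 0.05/0.158 = 0.32 to 0.15/0.095 = 1.58. The residual variance pooled over 60 women rises by about d²/60, so the standard error ratio is √(1 + d²/(60s²)):
- s = 0.5, d = 1.0: √(1 + 1/15) = 1.03
- s = 0.4, d = 2.0: √(1 + 4/9.6) = 1.19
- s = 0.3, d = 3.0: √(1 + 9/5.4) = 1.63

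**3. One such woman in every arm.** The expected within-arm variance becomes s² + d²/20, so the ratio is √(1 + d²/(20s²)):

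| SD | d = 1.0 | 1.5 | 2.0 | 2.5 | 3.0 |
|---|---|---|---|---|---|
| 0.3 | 1.25 | 1.50 | 1.80 | 2.11 | 2.45 |
| 0.4 | 1.15 | 1.31 | 1.50 | 1.72 | 1.95 |
| 0.5 | 1.10 | 1.20 | 1.34 | 1.50 | 1.67 |

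Exact doubling needs d = s√60 = 7.75 SDs, which is 2.3 points at s = 0.3, 3.1 at 0.4 and 3.9 at 0.5. A simulation of the planned regression (3 × 20 women, 8 covariates unrelated to outcome, 2,000 runs) agreed: 2.12 at s = 0.3 and d = 2.5, and 1.50 at s = 0.4 and d = 2.0. At 24 per arm the ratios are slightly lower, for example 1.97 instead of 2.11.

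**4. How likely each pattern is.** At prevalence p, at least one of 60 women has diabetes with probability 1 − (1 − p)^60, and every arm has at least one with probability [1 − (1 − p)^20]³.

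| p | At least one in trial | At least one in every arm |
|---|---|---|
| 1% | 45% | 0.6% |
| 2% | 70% | 4% |
| 5% | 95% | 26% |

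**5. Effect of adding baseline HbA1c** (simulated, one such woman per arm, assumed baseline to 6-month correlation 0.6 in the other women). If her gap is the same at both visits, the inflation falls to between about 1.05 and 1.1. If the gap is 1.0 at baseline and 2.5 at 6 months, it stays at about 1.7 (s = 0.3) or 1.5 (s = 0.4).

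**The case against.** The strongest reply is that the size of the problem depends wholly on assumptions. This stands. The documents give no SD, HbA1c level or prevalence. A reader might infer that the standard error would roughly double, but that needs one such woman in every arm together with a small SD and a large gap. A single such woman in the trial raises it only 1.03 to 1.63 times over the same assumed range.

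A second reply is that adjusting for baseline HbA1c deals with most of the problem without changing the population. This stands when her gap is stable across visits and only partly when it is not. The plan does not include that covariate, so the reply supports a change rather than the current text.

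Third, the general exclusions leave room for judgement at screening. True, so the list *could* admit such a woman; it does not follow that a site *would* enrol her. Equally, those items do not name diabetes, and two screeners could read them differently.

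Fourth, recruitment runs through a "maternal fetal medicine specialist, sees pregnant women at this location", and a reader might infer that diabetes is common among those screened. The documents report no such prevalence. Nor do they support saying that her HbA1c would respond only to medical treatment and not to a diet and exercise programme. That she cannot progress to diabetes concerns the trial's purpose, not the analysis, since diabetes incidence is not an outcome.

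Finally, this is a feasibility pilot not sized for power, and if the next trial used the same eligibility, the wider variance would be the right one. Both points limit the consequence. Neither removes the need to say whether these women are eligible.

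**Conclusion.** The point holds as a gap in eligibility and in the Aim 2 model, worth a cheap correction. Neither list excludes diabetes diagnosed before pregnancy, HbA1c is a primary outcome, and the model has no term that clearly absorbs such a woman's higher value. The more plausible pattern is an uneven one, with a shift of 0.05 to 0.15 points in one arm's mean, about a third to one and a half times the clean standard error of a difference. An increase in the standard error of about 1.1 to 2.5 times belongs to the less likely pattern of one such woman in every arm. All of this rests on an assumed SD of 0.3 to 0.5, a gap of 1.0 to 3.0 points and 20 women per arm. The documents do not support a flat statement that precision would be halved.

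**What to change.** 1. Add *type 1 or type 2 diabetes diagnosed before this pregnancy* to the exclusions in Table 1 and in Section IV.A.a. State that women who develop gestational diabetes after entry stay in the trial and the analysis. The words *before this pregnancy* also keep them out of the Section II.D review of participants who develop an exclusion condition after enrolment.
2. Add baseline HbA1c, already scheduled in Table 5, to the Aim 2 HbA1c model, and define pre-diabetes status.
3. If a woman with pre-existing diabetes is already enrolled, keep her in the trial and report Aim 2 HbA1c with and without her.

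The cost is one eligibility line in two places, one covariate and possibly one extra analysis. The status can be taken from history at screening. The downside is a small loss of eligible women and slightly narrower generalisability. If the sponsor wants these women in the trial, it should say so; items 2 and 3 then apply to all of them.
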